- Evidence of clinical benefit defined as a transfusion reduction of ≥ 2 pRBC units/8 weeks compared to the baseline (for any consecutive 8-week period within the 12 weeks immediately preceding Day 169 and every 24 weeks thereafter [ie, Day 337, Day 505, etc.]).
- Absence of disease progression per International Working Group (IWG) criteria for altering natural history of MDS ([Cheson, 2006](#)) based on central morphological assessment of bone marrow, peripheral blood and cytogenetics results.

Based on the outcome of these assessments, subjects will either be discontinued from treatment with IP, undergo End of Treatment (EOT) Visit evaluations and enter the Post-treatment Follow-up Period or continue open-label treatment with their assigned IP as long as the above criteria continue to be met or until the subject experiences unacceptable toxicities, withdraws consent, or meets any other discontinuation criteria.

Post-treatment Follow-up Period:

All subjects who have received at least one dose of IP should undergo EOT and 42-Day Follow-up evaluations.

This includes (but is not limited to) the collection of adverse events (AEs), concomitant drugs and RBC-transfusion data (until 8 weeks after last dose of IP or the EOT Visit, whichever occurs later).

In addition, subjects will continue to be followed for 5 years from the date of the first dose of IP, or 3 years from the last dose (whichever occurs later), for monitoring for other malignancies/pre-malignancies and progression to AML along with data collection of subsequent MDS therapies, and overall survival unless the subject withdraws consent from the study, dies or is lost to follow-up. For that purpose, subjects will be followed after treatment every 12 weeks for 3 years from the date of last dose of IP and every 6 months thereafter, if applicable.

An antidrug antibodies (ADA) sample(s) may be required in the Post-treatment Follow-up Period for subjects assigned to the luspatercept arm, who terminate the Treatment Period with less than 1 year of ADA monitoring if a subject is ADA positive at the time of treatment discontinuation.

The study will be conducted in compliance with International Council for Harmonisation (ICH) Good Clinical Practices (GCPs).

Study Population

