Adult subjects (≥ 18 years) with anemia due to a IPSS-R very low, low, or intermediate risk MDS according to the WHO 2016 classification and a bone marrow blast count of $< 5\%$ (Arber, 2016; Greenberg, 2012), who are ESA naïve with endogenous sEPO levels of < 500 U/L and who require RBC transfusions (ie, 2 to 6 units/8 weeks of pRBCs confirmed for a minimum of 8 weeks immediately preceding randomization).

Length of Study

The expected duration of the study is approximately 8 years, which consists of approximately 2 years of enrollment, approximately 1 additional year of luspatercept or epoetin alfa treatment after the last subject is randomized, and 5 years of follow up from first dose of IP, or 3 years from last dose (whichever occurs later), to complete the Post-treatment Follow-up Period.

The End of Trial is defined as either the date of the last visit of the last subject to complete the post-treatment follow-up, or the date of receipt of the last data point from the last subject that is required for primary, secondary and/or exploratory analysis, as prespecified in the protocol, whichever is the later date.

The sponsor may end the trial when all key endpoints and objectives of the study have been analyzed and the availability of a roll-over protocol exists into which subjects remaining on study may be consented and continue to receive access to luspatercept and/or complete long-term follow-up. Such a protocol would be written for a compound that would not yet be commercially available.

Study Treatments

Eligible subjects will be randomized by a central randomization procedure using integrated response technology (IRT) at a 1:1 ratio to one of the below treatment arms:

- **Experimental Arm:** luspatercept (ACE-536): starting dose of 1.0 mg/kg subcutaneous injection every 3 weeks (21 days; Q3W). Dose levels can be increased in a stepwise manner beyond the starting dose to 1.33 mg/kg, and up to a maximum of 1.75 mg/kg .

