	Progression to AML	Number and percentage of subjects progressing to AML; time to AML progression	Randomization through 5 years from first dose or 3 years from last dose (whichever occurs later)
	Overall survival	Time from date of randomization to death due to any cause	Randomization through 5 years from first dose or 3 years from last dose (whichever occurs later)
Exploratory	Molecular and cellular markers in the bone marrow and/or in peripheral blood	Evaluation of biomarkers that may potentially impact luspatercept efficacy, predict response or relapse, help to better understand MOA and/or provide further prognostic classification of MDS subtypes. Molecular markers (eg, SF3B1) include evaluation of MDS-associated gene mutations and their impact on drug efficacy, clinical response or relapse, drug MOA and prognostication of MDS.	Baseline through End of Treatment
	Healthcare resource utilization	Evaluation of healthcare resource use (eg, hospitalization) associated with investigational product (IP) during study	Screening through Week 24
	Health-related quality-of-life (HRQoL)	Description of QUALMS-P and Treatment Satisfaction	Screening through Week 24
	Exposure-response relationship.	Exposure-response relationship for selected endpoints of efficacy and safety.	Randomization through 1 year post first dose
	SARS-CoV-2 serology	Exploratory measurements of SARS-CoV-2 serology (anti-SARS-CoV-2 IgG or total antibody), from serum samples collected at baseline, D169, D337 and EOT, and impact on safety profile of luspatercept.	Screening through 42 days post last dose

Abbreviations: ADA = antidrug antibodies; AE = adverse event; AML = acute myeloid leukemia; D = Day; EORTC QLQ-C30 = European Organization for Research and Treatment of Cancer Quality-of-Life Questionnaire; EOT = end of treatment; FACT-An = Functional Assessment of Cancer Therapy – Anemia; HI-E = hematologic improvement – erythroid response; IgG = immunoglobulin G; IWG = International Working Group; MDS = myelodysplastic syndromes; MOA = mechanism of action; PK = Pharmacokinetics; QUALMS-P = Quality of Life in Myelodysplasia Scale - Physical Burden; RBC = red blood cell; RBC-TI = red blood cell transfusion independence; SARS-CoV-2 = severe acute respiratory syndrome coronavirus 2.

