6.3.2 Long-term Follow-up

Transfusion data collection will continue until 8 weeks from the date of last dose of IP or from the date of the EOT Visit (whichever is later) ([Section 6.4.1](#)). Subjects should also be followed via telephone contact by the site to verify if transfusions were given outside of the investigative site.

Antidrug antibodies sample(s) may be required in the Post-treatment Follow-up Period for subjects assigned to the luspatercept arm, who terminate the Treatment Period with less than 1 year of ADA monitoring if a subject is ADA positive at the time of treatment discontinuation ([Section 6.6](#)).

An additional pregnancy test is to be performed 12 weeks (± 7 days) from the date of last dose of IP for FCBP ([Section 6.1.14](#)).

All subjects discontinued from protocol-prescribed therapy for any reason should be followed for the below events/therapies for 5 years after the first dose of IP, or 3 years from the last dose (whichever occurs later), or until death, lost to follow-up or withdrawal of consent from the study.

- Progression to AML and other malignancies/pre-malignancies (please refer to [Section 6.1.19](#) and [Section 10.5](#) for details)
- Survival (date and cause of death)
- and subsequent MDS therapies

Subjects may be followed via telephone contact by the site for collection of the above data every 12 weeks for the first 3 years from the date of last dose of IP and every 6 months thereafter (if applicable) until 5 years after the first dose of IP, or 3 years from the last dose (whichever occurs later), or until death, lost to follow-up or withdrawal of consent from the study. Refer to [Table 3](#).

Data regarding subsequent MDS therapies, determination of AML progression and other malignancies/pre-malignancies, and date and cause of death will be recorded in the eCRF. The investigator must make every effort to obtain information regarding the subject's survival status before determining the subject is lost to follow-up. If the subject is discontinued from Long-term Follow-up, the reason for discontinuation should be recorded on the End of Study eCRF.

Long-term follow-up may be conducted by record review (including public records if allowed by local regulations) and/or telephone contact with the subject, family, or the subject's treating physician.

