9 STATISTICAL CONSIDERATIONS

9.1 Overview

This is a Phase 3, multicenter, randomized, open-label, active-controlled study. The primary objective of the study is to evaluate efficacy in the two treatment arms, luspatercept compared with epoetin alfa, for the treatment of anemia due to IPSS-R very low, low, or intermediate risk MDS in ESA naïve subjects who require RBC transfusions.

The final analysis will be performed when all randomized subjects have completed 24 weeks of treatment or discontinued before 24 weeks.

Additional follow-up analysis for efficacy and safety will be performed when all subjects have been followed for 5 years from the date of the first dose of IP, or 3 years from last dose (whichever occurs later) during the Post-treatment Follow-up Period of the study.

The design of the study, including the proposed targeted subject population, study endpoints, and statistical plan, is discussed below.

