9.7.2 Secondary Efficacy Analyses

The secondary efficacy endpoints will be analyzed and reported at the time of the analysis of the primary efficacy endpoints.

Secondary endpoints will be analyzed descriptively, unless otherwise specified, and will be based on the ITT population. Kaplan-Meier methods will be used to estimate curves for time to event secondary variables. Count, percentages, and 95% confidence interval will be used to describe categorical secondary variables.

Gate-keeping method will be used to control the overall Type I error rate for the following secondary endpoints in the order of:

- HI-E response (Week 1 to 24)
- RBC-TI for 24 weeks (Week 1 to 24)
- RBC-TI ≥ 12 weeks (Week 1 to 24)

After the result from the primary efficacy endpoint shows statistical significance, RBC-TI for 24 weeks in Week 1 to 24 will be tested for significance at the one-sided significance level of 0.021 only if both primary endpoint and HI-E response in Week 1 to 24 are significant. RBC-TI ≥ 12 weeks in Week 1 to 24 will be tested for significance at the one-sided significance level of

0.021 only if the results for primary endpoint, HI-E in Week 1 to 24, and RBC-TI for 24 weeks in Week 1 to 24 are all significant. The testing procedure above will be implemented strictly in order to control the overall one-sided Type I error rate of 0.025 due to multiplicity.

Other secondary endpoints will be analyzed without employing methods for controlling the type one error rate. Any statistically significant treatment effect on these secondary endpoints cannot be interpreted as confirmatory, but rather informative.

RBC transfusion independence (RBC-TI) for 24 weeks is defined as the absence of any RBC transfusion from Week 1 to the end of Week 24. Subjects discontinued from the Treatment Phase prior to finishing Week 24 will be counted as non-responders.

Mean hemoglobin change over 24 weeks is defined as the mean hemoglobin change over the 24-week period of Week 1 through Week 24 compared to baseline

Hematologic improvement – erythroid response (HI-E) per IWG (Cheson, 2006) is defined as proportion of subjects meeting HI-E criteria sustained over any consecutive 56-day period over the first 24 weeks from Week 1. Subjects discontinued from the Treatment Period without achieving HI-E will be counted as non-responders.

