Time to HI-E will be summarized only for subjects who achieve HI-E response. It is defined as time from Week 1 to first onset of achieving HI-E. It will be summarized only for subjects who achieve HI-E within the first 24 weeks from Week 1.

RBC-TI for ≥ 12 weeks (84 days) is defined as the proportion of subjects achieving RBC-TI for ≥ 84 days during any consecutive 84-day period from Week 1 through Week 24.

Duration of RBC-TI ≥ 12 weeks (84 days) is defined as the longest RBC-TI period for subjects who achieve RBC-TI ≥ 12 weeks from Week 1 through Week 24. Subjects who maintain RBC-TI through the end of the Treatment Period or at the time of analysis will be censored at the date of treatment discontinuation, date of analysis or death, whichever occurs first.

Time to RBC-TI ≥ 12 weeks (84 days) will be summarized only for subjects who achieve RBC-TI ≥ 84 days from Week 1 through Week 24. It is defined as the time between Week 1 and the date onset of TI is first observed (ie, Day 1 of 84 days without any RBC transfusions).

Time to first RBC transfusion is defined as time from Week 1 to first RBC transfusion on treatment. Subjects who maintain RBC-TI through the end of the Treatment Period or time of analysis will be censored at the date of treatment discontinuation/time of analysis or death, whichever occurs first.

RBC transfusion burden on treatment is defined as total number of pRBC units transfused within the first 24 weeks of treatment since Week 1.

RBC-TI for ≥ 56 days (8 weeks) is defined as the proportion of subjects achieving RBC-TI for ≥ 56 days during any consecutive 56-day period from Week 1 through Week 24.

RBC-TI for a consecutive 24-week period is defined as the proportion of subjects achieving RBC-TI for ≥ 168 days during any consecutive 168-day period from Week 1 through Week 48.

Progression to AML: time to AML progression is defined as the time between randomization and first diagnosis of AML as per WHO classification of $\geq 20\%$ blasts in peripheral blood or bone

marrow. Subjects with diagnosis of AML will be considered to have had an event. Subjects who have not progressed to AML at the time of analysis will be censored at the last assessment date which does not indicate progression to AML.

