Overall survival (OS) is defined as the time between randomization and death/censored date. Subjects who die, regardless of the cause of death, will be considered to have had an event. Subjects who are alive at the time of analysis will be censored at the last assessment date at which the subject was known to be alive. All subjects who were lost to follow-up will also be censored at the time of last contact.

Full analysis details will be included in the SAP.

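### After year 5 only subjects treated for more than 2 years remain at risk for overall survival and AML, so the Kaplan-Meier tail depends on response; the curves should stop at a common 5 years

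*Combined protocol and SAP*

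**What the plan says.** **Follow-up.** Section 6.3.2 follows subjects for survival and AML "for 5 years after the first dose of IP, or 3 years from the last dose (whichever occurs later"), unless they die, withdraw or are lost. Table 2 gives both endpoints the same time frame, and Section 6.1.19 repeats it for AML.

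**Staying on drug.** At Day 169 and every 24 weeks, subjects must show a reduction of at least 2 pRBC units per 8 weeks from baseline and no IWG progression (Section 6.4.2). Those who qualify "continue open-label treatment with their assigned IP as long as the above criteria continue to be met" (Protocol Summary). No maximum treatment length is stated.

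**Estimation.** In Section 9.7.2, "Kaplan-Meier methods will be used to estimate curves for time to event secondary variables". For survival, "Subjects who are alive at the time of analysis will be censored at the last assessment date" on which they were known to be alive. For AML, "Subjects who have not progressed to AML at the time of analysis will be censored at the last assessment date" that shows no progression. No truncation time or common cut-off is given, and full details are deferred to the SAP.

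**Timing.** Section 9.1 plans an additional efficacy and safety analysis "when all subjects have been followed for 5 years from the date of the first dose of IP, or 3 years from last dose", whichever is later. That is the analysis that would use data past year 5.

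**The concern.** Kaplan-Meier assumes that subjects censored at a given time have the same later prognosis as those who stay under observation. Here, who leaves at year 5 and who stays is decided by time on treatment, and time on treatment is decided by benefit and absence of progression. Past year 5 the curve starts from the whole cohort's survival but falls at the rate of long-treated subjects alone.

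The link is close for AML. Rising marrow blasts meet the progression criteria in Appendix D, and confirmed peripheral blasts of 1% or more lead to discontinuation under Tables 5 and 7. For survival, Section 1.1.1.2 says that transfusion dependency worsens survival, and Section 1.1.1.5 associates longer transfusion independence with better survival.

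At stake is how the late part of the long-term curves is read, including an AML curve that serves a safety purpose. If time on drug differs by arm, the selection after year 5 differs by arm too, and the two tails are not comparable.

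**Working it through.** **1. The plan's own figure.** No event number, power or precision is stated for survival or AML. The only sized quantity is 350 subjects for the primary endpoint (36% vs 20%, one-sided 0.025, 90% power, odds-ratio test). It reproduces: ln[(0.36/0.64)/(0.20/0.80)] = ln 2.25 = 0.811; variance term 1/(0.36×0.64) + 1/(0.20×0.80) = 10.59; n = (1.960+1.282)² × 10.59 / 0.811² ≈ 169.2, so 170 per arm or 340 in total, with 90.9% power at 175 per arm. Nothing below depends on it.

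**2. Who is followed past year 5.** Let L be years from first to last dose. Follow-up is F = max(5, L + 3), and L + 3 > 5 only if L > 2.

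| L (years) | 1 | 1.5 | 2 | 2.5 | 3 | 4 |
|---|---|---|---|---|---|---|
| F (years) | 5 | 5 | 5 | 5.5 | 6 | 7 |

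At any time t > 5, only subjects with L > t − 3 are at risk.

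**3. How far the tail reaches as planned.** The Protocol Summary expects about 2 years of enrollment and about 1 further year of treatment after the last randomization. For a subject enrolled a years after study start, L is at most 3 − a, so F is at most max(5, 6 − a): 6 years for a = 0, 5.5 for a = 0.5, and 5 for a of 1 or more. Only first-year enrollees can pass year 5, and nobody passes year 6 unless treatment outruns that timetable.

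**4. Size for survival, two-class model.** The documents give neither the share treated for more than 2 years nor its hazard, so both are assumed. A share f has hazard hλ and the rest have λ, with λ set so that overall median survival is 5.3 years (Appendix C, Low).

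- True: S(t) = (1−f)e^(−λt) + f e^(−hλt)
- Kaplan-Meier for t > 5: S(5) × e^(−hλ(t−5))

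Example, f = 0.25 and h = 0.5: λ = 0.153 and S(5) = 0.520. True S(6) is 0.457; Kaplan-Meier reads 0.520 × e^(−0.0765) = 0.481, or 2.4 points too high.

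Year 6, Kaplan-Meier vs true (difference in points):

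| h | f = 15% | f = 25% | f = 35% |
|---|---|---|---|
| 1.0 | 0.456 vs 0.456 (0) | 0.456 vs 0.456 (0) | 0.456 vs 0.456 (0) |
| 0.7 | 0.472 vs 0.456 (1.6) | 0.471 vs 0.457 (1.4) | 0.469 vs 0.457 (1.2) |
| 0.5 | 0.484 vs 0.457 (2.7) | 0.481 vs 0.457 (2.4) | 0.479 vs 0.458 (2.1) |
| 0.3 | 0.496 vs 0.458 (3.8) | 0.493 vs 0.459 (3.4) | 0.490 vs 0.460 (3.0) |

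This model keeps every long-treated subject at risk after year 5, whereas the rule needs more than 3 years on drug to be at risk at year 6.

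**5. Second model.** A simulation of 400,000 subjects applied the rule exactly, with a shared frailty linking treatment duration and death, 19–30% treated for more than 2 years, and no calendar stop to treatment. Of those alive at year 5, 24–47% were still followed (about 44–85 of 350). With no link the overstatement was zero. With a link it was 1.5–2.0 points at year 6.

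**6. At year 5.** Kaplan-Meier equalled true survival in every simulated scenario (for example 0.520 vs 0.520, 0.518 vs 0.518, 0.515 vs 0.515).

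The size for AML was not calculated.

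**The case against.** The strongest reply is that the effect is small and nothing hangs on it. Survival and AML lie outside the gate-keeping sequence and are descriptive. The censoring sentence is standard; the cause is the follow-up rule combined with the absence of a common cut-off. A truncation rule may sit in the SAP to which Section 9.7.2 defers. All of this stands, and it limits the point to a cheap improvement.

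Several stronger readings are tempting but not supported:

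- **The curves overstate survival.** A reader might infer this as fact. It is an inference from the background sections about this trial's subjects; if treatment duration and hazard are unrelated, the error is zero.
- **The whole curve describes responders.** Its level at year 5 is that of the full cohort. Only the later slope is selected.
- **The error is large by year 8.** The two-class model gives 2.8–9.4 points there for h from 0.7 to 0.3, and the linked simulation 4–6. But being at risk at year 8 needs more than 5 years on drug, against at most about 3 as planned. The statement that "The expected duration of the study is approximately 8 years" describes the whole study; Section 3.2 puts a subject's participation at about six years.
- **Median survival will read too long.** That requires a true median beyond year 5. Appendix C gives 8.8, 5.3 and 3.0 years for the three eligible risk groups, and the mix is unknown.
- **A hazard ratio or test is biased.** The protocol specifies none for these endpoints.
- **The open-ended trigger should be replaced by a fixed date.** An analysis 5 years after the last first dose could precede completion of 3 years after last dose in the longest-exposed subjects, in an analysis that also covers safety. Sections 3.3 and 13.8 already allow the sponsor to close the trial through a roll-over protocol.

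**Conclusion.** The point holds on structure. After year 5 the risk set contains only subjects treated for more than 2 years, who had to keep meeting benefit and no-progression criteria, and the Kaplan-Meier plan does not account for this. The direction is plausible on the protocol's own background but not established. For survival the size is about 1 to 4 points too high at year 6, assuming 15–35% long-treated, a hazard ratio of 0.7 to 0.3 for them against the rest, and an overall median of 5.3 years. It is zero with no link, and larger only if treatment runs past the planned timetable. The exposure is in the additional follow-up analysis: results reported with the primary analysis are affected only if that analysis already holds follow-up past year 5. No confirmatory conclusion changes.

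**What to change.** In Section 9.7.2 (and the SAP), censor overall survival and time to AML administratively at 5 years from randomization for the Kaplan-Meier estimates and for any between-arm comparison. Report events after year 5 descriptively, by arm, with numbers at risk. First dose is due within 3 days of randomization, so this cut-off falls within the minimum planned follow-up of every treated subject.

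Keep the current follow-up duration and the current trigger for the additional follow-up analysis, so that late safety data in the longest-exposed subjects are still analysed.

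The cost is wording only, with data collection unchanged. The downside is that the few late events in long-treated subjects leave the main curve.
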